**7.4.10 Visit 7 (Study Day 60 ± 3 days)**

*Postoperative Day 59 ± 3 days*

Approximately 2 months after surgery, a clinic visit will be conducted for assessment of AEs and surgical site examination. During the clinic visit, the following trial procedures will be performed:

- Surgical Site Examination and Assessment of Surgical Site AEs including bruising, bleeding or drainage from the incision(s), hematoma, dehiscence, infection and abnormal healing
- Adverse Events – All reported AEs will be documented as noted in [Section 9.3](#)
- Review of Concomitant Medications – As noted in [Section 7.6](#), all medications (including pain medications) taken since the last visit will be documented.
- Physical Exam (including weight)
- 12-lead ECG
- Vital Signs
- Safety Laboratory Tests (chemistry, hematology, urinalysis)

All AEs, of whatever etiology and location, occurring after informed consent should be recorded on the eCRF as an AE. All AEs will be followed until resolution unless the patient is lost to follow up. Resolution means no further changes in the event are expected, i.e., the point at which a subject experiencing such an AE is appropriately treated and stabilized even though they may continue to experience lingering sequelae that may never resolve.

**NOTE:** Patients enrolled prior to IRB approval of Amendment 5 will not need to return for a Study Day 60 visit.

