### 9.3.2 Adverse Event Reporting

All events that meet the definition of an AE that occur in the period from when the patient has signed the informed consent form (ICF) through trial completion (final visit), or early termination, must be recorded on the adverse event eCRF. All SAEs will be recorded on the appropriate eCRF and on the Serious Adverse Event Report Form from the time written informed consent has been obtained through trial completion (final visit), or early termination.

At each contact between the investigative site and the patient (visit or phone), after the patient has had an opportunity to spontaneously mention any problems, the Investigator should inquire about the occurrence of AEs. The following are examples of open-ended questions that may be used to obtain this information:

“How are you feeling?”

“Have you had any medical problems since your last visit/assessment?”

“Have you taken any new medicines, other than those given to you in this study, since your last visit/assessment?”

All AEs and SAEs will be documented in source records at each assessment time or when otherwise volunteered by the patient and recorded on the appropriate eCRF. Information to be collected includes the nature, date and time of onset, severity, duration, relationship to test drug, and outcome of the event. Even if the Investigator assesses the AE as not reasonably attributable to the test drug, its occurrence must be recorded in the source documents and reported on the eCRF along with the assessment of association.

The Investigator will treat the patient as medically required, and this may extend beyond the duration of the trial. The Investigator will record treatment and medications required to treat AEs on the appropriate eCRF(s). All AEs will be followed until resolution (no further changes in

the event are expected, i.e., the point at which a subject experiencing such an AE is appropriately treated and stabilized even though they may continue to experience lingering sequelae that may never resolve) unless the patient is lost to follow up.

DURECT will evaluate all AEs with respect to seriousness, causality and expectedness in accordance with [Directive 2001/20/EC](#) (3) and FDA Guidelines. The expectedness of an AE will be determined according to the current version of the Investigators Brochure.

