### 9.3.3 Reporting of Serious Adverse Events

Regardless of causality, the investigator must complete and submit an SAE form to **CCI** Safety Surveillance within 24 hours of knowledge of the event for all serious adverse events.

**SAEs will be reported to:** **CCI** Safety Surveillance

**Fax:** **PPD** (toll free)

The Investigator must indicate the SAE's relationship to test drug and sign the SAE form. When additional relevant information (final diagnosis, outcome, results of specific investigations, etc.) becomes available, the investigator must record that follow-up information in the eCRF. Follow-up information should be recorded according to the process used for reporting the initial event as described above. The investigator will follow all reportable events (i.e., SAEs) until resolution. Resolution means no further changes in the event would be expected, i.e., the point at which a subject experiencing such an AE is appropriately treated and stabilized even though they may continue to experience lingering non-serious sequelae that may never resolve.

Safety Surveillance will follow all SAEs until resolution (no further changes in the event are expected, i.e., the point at which a subject experiencing such an AE is appropriately treated and stabilized even though they may continue to experience lingering sequelae that may never resolve). Safety Surveillance will report all SAEs to DURECT within 1 business day of receipt.

All serious adverse events will also be reported on the AE CRF and concomitant medications administered in association with the serious AE will be documented on the CM CRF.

If a serious adverse event occurs and comes to the attention of the Investigator after trial completion/termination within 60 days of test drug dosing or within 30 days of the last trial visit (whichever occurs later), it must be reported immediately to Safety Surveillance in the same manner as the serious adverse events occurring during the trial. Investigators are not obligated to actively seek AEs from former study participants.

The Investigator must report SAEs to the IRB/IEC (per the IRB/IEC guidelines/SOPs), including all SAEs that have occurred at the investigative site and all trial related SAEs that have resulted in an expedited safety report to a regulatory agency. Concurrently, the Investigator must send DURECT documentation of such IRB/IEC notification or if reporting is not required

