### **11.10 Statistical Analysis of Safety Endpoints**

#### **11.10.1 Safety Variables and Summaries**

Safety summaries will be based on the safety population. The safety population will include all subjects treated with SABER®-Bupivacaine 5 mL (660 mg bupivacaine base) or 0.9% sterile normal saline 5 mL (placebo) in Part 1; and all subjects treated with SABER®-Bupivacaine 5 mL or 15 mL of 0.5% bupivacaine HCl in Part 2. It will include summaries in the form of tables and patient listings by three treatment arms; SABER®-Bupivacaine 5 mL (660 mg bupivacaine base), 15 mL of 0.5% solution bupivacaine HCl (75 mg) or 0.9% sterile, normal saline 5 mL (placebo).

Safety variables include:

- Subject incidence rate of adverse events (both pre-specified patient-reported AEs solicited on LogPad through Study Day 4 [POD 3], as well as spontaneous AEs reported either by patient or investigator)

- Subject incidence rate of solicited AEs occurring in the first 6 hours after dosing of test drug.
- Time to the first occurrence of the solicited AEs
- Time to PACU discharge
- Change in standard 12-lead ECG at Screening, Visit 6 (Study Day 29), and Visit 7 (Study Day 60)
- Change in safety Laboratory Tests (serum chemistry, hematology, urinalysis) (Screening, Study Day 4, Study Day 29, Study Day 60)
- Change in vital Signs (heart rate, blood pressure, temperature, respiratory rate) (at each scheduled visit) and height, weight, BMI (Screening, Study Day 29, Study Day 60)
- CCI 

The subject incidence rate (number and percentage) of treatment emergent adverse events will be tabulated in each treatment group by MedDRA System Organ Class and Preferred Term. Summaries will also be presented by the severity of the adverse event and by relationship to test drug.

The individual rate of solicited patient-reported AEs (dizziness, somnolence, constipation, nausea, vomiting, pruritus, headache, dysgeusia, hypoesthesia, and paresthesia) will be derived. The risk ratio and 95% confidence interval (CI) for the individual AE rate will be presented with saline placebo and bupivacaine HCl as the control groups. For example, if the 95% CI for the risk ratio contains 1, the AE risk is considered comparable between the active and control groups.

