Time to the first occurrence of the solicited AEs will be analyzed by the Kaplan Meier method. For subjects who do not have the AE, the observation will be censored in the analyses. Median time and 95% confidence interval (CI) will be determined.

The change in safety laboratory, ECG and vital signs parameters from baseline will be analyzed by shift tables. Descriptive statistics (means, medians, SD, minimum/maximum) for the safety variables and change from baseline will be summarized. Subjects found to have abnormal safety values considered clinically significant will be summarized.

The presence/absence of surgical site AEs (see definitions in [Section 9.2.6](#)) will be tabulated by treatment and study visit. The overall rate of each AE across study visits will be tabulated by treatment. The risk ratio and 95% CI will be derived for each AE. Known risk factors related to wound healing, such as being diabetic or having higher BMI, may be used for adjusted relative risk if they are not balanced by randomization alone. Time to the first occurrence of each AE

will be derived from the end of surgery. The data will be censored for subjects who do not have the AE. The median, 95% CI, 25th and 75th percentile for the time to each AE will be summarized by treatment. The time to resolution of each AE will also be derived and summarized.

CCI

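### To the extent that Part 1 patients skip the Day 60 visit, the pooled SABER safety arm has less late AE follow-up than HCl and more than saline; comparative AE rates should be made within Part (minor)

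*Combined protocol and SAP*

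**What the plan says.** Section 7.4.10 adds a clinic visit at Study Day 60 ± 3 with a surgical-site examination and AE review, then exempts some patients: "Patients enrolled prior to IRB approval of Amendment 5 will not need to return for a Study Day 60 visit". Their last planned visit is therefore Visit 6, Study Day 29 ± 3 (section 7.4.9).

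Section 9.3.2 requires that AEs arising from consent "through trial completion (final visit), or early termination, must be recorded on the adverse event eCRF". After that, section 9.3.3 keeps only SAEs reportable, up to 60 days after dosing or 30 days after the last visit, whichever is later. It adds: "Investigators are not obligated to actively seek AEs from former study participants".

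The synopsis places about 90 patients in Part 1, before the switch to Part 2. Section 5.4.1 gives SABER and saline in Part 1, and SABER and bupivacaine HCl in Part 2. The safety population joins both Parts (section 11.4).

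For the output, section 11.10.1 says: "It will include summaries in the form of tables and patient listings by three treatment arms". The three arms are SABER, HCl and saline, so SABER from both Parts forms one arm. On AEs in general: "The subject incidence rate (number and percentage) of treatment emergent adverse events will be tabulated in each treatment group". Surgical-site AEs "will be tabulated by treatment and study visit", and in addition: "The overall rate of each AE across study visits will be tabulated by treatment". A comparative measure is planned for them as well: "The risk ratio and 95% CI will be derived for each AE". The visible text sets no common onset cut-off, adjustment for length of follow-up, split by Part, or denominator for Visit 7. Parts of the section are redacted.

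**The concern.** A crude percentage treats every patient in the denominator as observed for the same time. Here some may be observed to about Day 29 and others to about Day 60. Any Part 1 exemption removes late follow-up from all of the exempt saline patients' arm, from only a fraction of pooled SABER, and from none of HCl. Late capture is then ordered saline, pooled SABER, HCl, from lowest to highest, because of the visit schedule and not the drug. Randomization does not protect these contrasts, because the pooled SABER arm crosses Parts.

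At stake is a small shift of known direction in the safety tables: in favour of SABER against HCl and against SABER versus saline. A confidence interval does not show it. It matters most for late, non-serious wound findings, where events are few and one missed event is visible.

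**Working it through.** **Inputs from the protocol.** Part 2: 132 evaluable patients per arm (section 5.4). Part 1: about 90 patients at 1:1 (section 11.3), so about 45 per arm. Pooled SABER is 45 + 132 = 177.

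**Plan's own figure.** The plan states no figure for AE capture. Its Part 2 size does reproduce: 264/0.96 = 275 against 274 stated, so 132 treated per arm is consistent.

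**Inputs not in the documents, varied here.** k = exempt patients per Part 1 arm (0 to 45); f = share of first events starting after Day 29; c = share of late events in exempt patients that is still captured. True risk ratio = 1. No Part 2 patient is exempt unless stated.

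**Overall AE rate or overall surgical-site rate.**

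Ratio vs HCl = 1 − f·k(1−c)/177.

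Ratio vs saline = [1 − f·k(1−c)/177] / [1 − f·k(1−c)/45].

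Example, f = 5%, k = 45, c = 0: f·k = 2.25. Vs HCl, 1 − 2.25/177 = 0.987. Vs saline, 0.9873/(1 − 2.25/45) = 0.9873/0.95 = 1.039.

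Example, f = 20%: f·k = 9. Vs HCl, 1 − 9/177 = 0.949. Vs saline, 0.9492/0.80 = 1.186.

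| k (c = 0) | Contrast | f = 5% | f = 10% | f = 20% |
|---|---|---|---|---|
| 15 | vs HCl | 0.996 | 0.992 | 0.983 |
| 15 | vs saline | 1.013 | 1.026 | 1.053 |
| 45 | vs HCl | 0.987 | 0.975 | 0.949 |
| 45 | vs saline | 1.039 | 1.083 | 1.186 |

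Capturing half of the late events (c = 0.5) roughly halves the shifts. At k = 0 every ratio is 1.

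**Against sampling error**, at an assumed 80% overall AE incidence and k = 45, with SE(log RR) = √[(1−p₁)/(n₁p₁) + (1−p₂)/(n₂p₂)]:

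- f = 20%, vs HCl: p = 0.759 (n = 177) and 0.80 (n = 132); SE = 0.061; |ln 0.949| = 0.052; about 0.9 SE.
- f = 20%, vs saline: p = 0.759 (n = 177) and 0.64 (n = 45); SE = 0.120; ln 1.186 = 0.171; about 1.4 SE.
- f = 5%: 0.013/0.058 = about 0.2 SE vs HCl, and 0.038/0.092 = about 0.4 SE vs saline.

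**Late-onset AEs alone** (not a planned output). Ratio vs HCl = 1 − k(1−c)/177. At c = 0 this is 0.97, 0.92, 0.83 and 0.75 for k = 5, 15, 30 and 45. The bound is 132/177 = 0.746, or 0.873 with half captured. If 43 rather than 45 Part 1 SABER patients are dosed, it is 132/175 = 0.754. If m patients per Part 2 arm are exempt as well, [(132−m)/177]/[(132−m)/132] = 132/177, so the bound does not move as long as some Part 2 patients have the visit. Vs saline, half of Part 1 exempt gives 0.873/0.5 = 1.746; with all of Part 1 exempt and nothing captured, the ratio is undefined.

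At an assumed 2% late risk and k = 45, 45 × 0.02 = 0.9 SABER events are missed and 132 × 0.02 = 2.64 are expected in each of the SABER and HCl arms. SE = √(1/2.64 − 1/177 + 1/2.64 − 1/132) = 0.863; |ln 0.746| = 0.293; about one third of an SE.

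**Within-Part contrasts.** SABER vs HCl within Part 2, and SABER vs saline within Part 1, have equal expected follow-up, because enrolment date is balanced by randomization within each Part. The null ratio is 1 in each.

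**The case against.** The strongest case is that the problem may be absent and is in any event small. The visible text does not tie Amendment 5 to the opening of Part 2, so k could be anything from 0 to 45; f, c and the late risk are not in the documents either. That stands, and the point is conditional on it.

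Existing provisions also narrow the exposure:

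- LogPad solicitation ends at Study Day 4 (section 7.5), so the one risk ratio that names saline and HCl as controls is unaffected.
- Late SAEs stay reportable, though passively.
- AEs with earlier onset are followed to resolution.
- Superficial incisional infection must by definition begin within 30 days (Appendix 5).
- Time-to-event summaries are censored (sections 11.6 and 11.10.1).
- Surgical-site AEs are also shown by visit, which separates Visit 7 findings, although its denominator is not given.

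All of this stands. What remains is mainly new non-serious AEs starting after about Day 29, in the crude percentages and in the overall surgical-site risk ratio.

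The omission also cannot be confirmed. Redacted text in section 11.10.1, or the separate SAP mentioned in sections 11.6 and 11.11, may already set a common window or a display by Part. If so, the sponsor need only point to it.

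**Conclusion.** The point holds in a conditional and minor form. To the extent that Part 1 patients are exempt from Day 60, the pooled SABER arm captures relatively fewer late new AEs than HCl and relatively more than saline, with no true difference. For overall rates the shift is small if few first events start late: 0.987 against HCl and 1.039 against saline at a 5% late share, even with all of Part 1 exempt.

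Four further inferences are not supported:

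- A reader might infer that SABER events are over-recorded against saline. They are not; the saline arm loses a larger share of its late events. For surgical-site AEs the saline contrast is itself inferred, because section 11.10.1 names no control for that risk ratio.
- A reader might take 0.75 as the bias in the safety comparison. It is a bound for late-onset AEs alone, which is not a planned output, and it needs every Part 1 SABER patient to be exempt and no late event captured.
- A reader might assume that all of Part 1 is exempt. The documents do not say so.
- A reader might dismiss the shift as always well inside sampling error. At a 20% late share with all of Part 1 exempt it is about 0.9 SE against HCl and 1.4 SE against saline, at an assumed 80% AE incidence.

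**What to change.** First confirm whether the SAP or the redacted text already sets a common AE window, and state how many Part 1 patients are exempt. If no window is set, before unblinding:

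1. Keep the pooled three-arm tables, with all AEs to each patient's last visit, and label them descriptive. Day 30 to 60 events then stay in the main tables, in line with the 60-day observation period in section 11.9.1.1.
2. Make the comparative AE rates and surgical-site risk ratios by Part: SABER vs HCl within Part 2, SABER vs saline within Part 1.
3. In by-visit tables, use patients scheduled for Visit 7 as the Visit 7 denominator.
4. If a pooled risk ratio is also shown, apply one fixed onset cut-off to all arms, such as onset on or before Study Day 29, and list onsets from Study Day 30 separately. Define the cut-off by study day and not by the visit: Visit 6 has a window of ± 3 days, so a visit-based rule paired with a Day 30 to 60 listing could drop an event or count it twice. Exempt patients seen on Day 26 to 28 would still lose up to three days, which is negligible here.

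No new data are needed. The costs are SAP wording, a few tables and some precision. For SABER vs HCl the standard error of the log risk ratio rises by about 7%: √(2/132)/√(1/177 + 1/132) = 0.1231/0.1150 = 1.07. The saline contrast rests on about 45 per arm, where the same calculation gives √(2/45)/√(1/177 + 1/45) = 0.2108/0.1669 = 1.26.

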**7.4.11 Early Termination Visit**

If a patient terminates the study early the following study procedures should be performed unless the patient withdraws consent. If a patient withdraws consent they will be encouraged to complete an early termination visit and AE follow-up:

- Surgical Site Examination and Assessment of Surgical Site AEs including bruising, bleeding or drainage from the incision(s), hematoma, dehiscence, infection and abnormal healing
- Adverse Events – All reported AEs will be documented as noted in [Section 9.3](#)
- Rescue Medication Reconciliation and Pill Count and collect Sponsor supplied acetaminophen
- Review of Concomitant Medications – As noted in [Section 7.6](#), all medications (including rescue medications) taken since the last visit will be documented.
- Physical Exam (including weight)

- 12-lead ECG
- Vital Signs
- Safety Laboratory Tests (chemistry, hematology, urinalysis)
- Inquire about Level of Activity including ambulation, sleeping, eating, current surgical wound pain, and return to work status - CCI [REDACTED]
- Medical Resource Utilization Assessment –including any hospital admissions, Emergency Department visits, or calls to their physician or surgeon with complaint of surgical complications, unmanageable pain, nausea/vomiting, or refills of rescue opioid prescription - CCI [REDACTED]

### 7.5 Electronic Diary (LogPad)

The LogPad is a handheld electronic device that records data entered by the patient and transfers it directly into a database maintained by the specific service provider. These devices will be provided to the patient by the investigative site at screening, the patient will bring the device with them on the day of surgery, the site will re-dispense the device to the patient in the PACU following surgery, and patients will return the device to the investigative site at Visit 4 (POD 7).

CCI [REDACTED]

The test drug administration time will be entered by the investigative site staff into the patient's LogPad via the Site Gateway within one hour post-dose.

The LogPad will be used to record pain intensity CCI [REDACTED] on movement (defined as sitting up, or attempting to do so, from a supine position) from Study Day 1 (day of surgery) through Study Day 4 (POD 3) (see [Section 8.2.1](#) CCI [REDACTED] oral rescue medication (oxycodone IR or acetaminophen) till Study Day 8 (POD 7), the associated pre-rescue CCI [REDACTED] on movement scores through Study Day 4 (POD 3), and the solicited AE checklist (which includes dizziness, somnolence, constipation, nausea, vomiting, pruritus, headache, dysgeusia, hypoesthesia, and paresthesia) from Study Day 1 to Study Day 4 (see [Table 2: Patient LogPad Schedule of Events](#)). If the patient reports an AE on the LogPad, an email alert will be sent to the investigative site personnel.

Data collected in the LogPad device will automatically transmit following completion of each assessment. Trial staff will access the transmitted data via the CCI [REDACTED]

CCI

## 7.6 Medication other than Test Drug

Any use of concomitant medications taken since 30 days prior screening will be recorded on the appropriate source document and concomitant medication (CM) eCRFs. This includes concomitant medications taken between screening and the surgery, medications taken during surgery, medications taken post-surgery (e.g. rescue medications, including titration and oral opioids, and acetaminophen), and for treatment of adverse events (AEs).

### 7.6.1 Prohibited Concomitant Medications

- Epidural or spinal analgesia, regional nerve blocks, intra-abdominal application of local anesthetics, and peri-incisional injection of local anesthetics other than the test drug have been **prohibited**.
- Use of systemic steroids, antidepressants, anticonvulsants or antiepileptics has been **prohibited** from screening until Visit 6 (Study Day 29).
  - Inhalational or topical corticosteroids are permitted
- Long-acting anticoagulants, such as warfarin, and long-acting antiplatelet drugs, such as clopidogrel, should be discontinued one week prior to surgery. Short-acting newer oral anticoagulants should be discontinued prior to surgery according to the labeled instructions. Low dose aspirin (81 mg) may be continued throughout surgery ([Joseph et al., 2015](#)). The anticoagulants and antiplatelet agents may be restarted after surgery when hemostasis is assured and there are no bleeding complications from surgery.
- NSAIDs, both prescribed (including Toradol® [ketorolac] Injection and Caldolor® [ibuprofen] Injection) and over the counter (OTC), are **not** allowed for one week prior to surgery and for 1 week after surgery (Study Day 8). Restricted OTC medications include (but are not limited to):
  - Aleve® (naproxen sodium), Advil® (ibuprofen), Motrin® (ibuprofen), Aspirin (except low dose [81 mg] aspirin taken as an antithrombotic), Alka-Seltzer®, Excedrin®, Midol®
- Other OTC combination products containing acetaminophen are **not** allowed for one week prior to surgery and for 1 week after surgery (Study Day 8). Restricted OTC medications include (but are not limited to):
  - Products containing acetaminophen for the following brands: NyQuil®, DayQuil®, Robitussin®, Benadryl®, Sudafed®, Theraflu®, and generic equivalents

- The use of combination and extended/sustained release opioid analgesic medications are prohibited from screening until the final visit (Study Day 60). Prohibited medications include (but are not limited to):
  - Combination products: Norco®, Lortab®, Percocet®, Vicodin®, Xodol®, Vicoprofen®, Zydone®, Percodan®, promethazine/codeine syrup, and generic equivalents
  - Extended/Sustained Release/Long-acting products: Avinza®, Butrans®, Dolophine®, Duragesic®, Embeda®, EXALGO®, Hysingla™ ER, Kadian®, Methadose™, MS Contin®, Nucynta® ER, Opana® ER, OxyContin®, Zohydro® ER, and generic equivalents
- Participants are prohibited from using investigational, unapproved, or recreational drugs. “Medical” marijuana and opioids (other than immediate-release oxycodone and IV fentanyl) may not be used from screening until the final visit (Study Day 60).
- Naltrexone should not be taken after surgery.

